Targeted physical examination																X		X				Sec. 8.3.1, Sec. 8.3.7		
Height	X																					Sec. 8.3.1		
Weight	X																			X		BMI to be taken only at Screening 1. Sec. 8.3.1		
Orthostatic VS (HR, BP)	X		X								X											Sec. 8.3.2.2.		
Semi-recumbent VS (HR, BP)	X		X					-X		X	X		X			X		X	X	X		Day 1 measurements will be at predose, 1- and 12-hours postdose. Sec. 8.3.2		
RR and body temperature	X		X		X			X		X	X		X							X		Sec. 8.3.2.		
12-lead ECG	X		X					X		X	X		X							X		Sec. 8.3.3.		
Standard Meals					X				X													Sec. 5.3.1.		
Domiciling			Х							X												Sec. 8.1.11		
MK-2060/Placebo Administration				X																		MK-2060/Placebo will be administered SC at Time 0. Refer to Sec. 6.2, 8.1.8 and the Study Pharmacy Manual for additional information on the preparation and administration of the study drug.		

Part 3																							
		Scheduled Time  Day 1 (hours post-																					
			Da	y I	(ho		s po	st-		Days													
Scheduled Timing	Screening 1	Screening 2 a	Predose	0	1	4	8	12	2 (D1 24 hrs)	3 (D1 48 hrs)	6 (D1 120 hrs) (±1 Day)	8 (D1 168 hrs)	11 (±1 Day)	14 (±1 Day)	21 (±2 Days)	28 (±3 Days)	42 (±4 Days)	60 (±5 Days)	90 (±5 Days)	120 Poststudy b (±5 Days)	134 Phone Follow-up c (±5 Days)	Notes	
Local Injection Site Reaction					X	X	X		X	X	X	X										Note: Participants who call the CRU to report an injection site reaction on Days 4, 5, and/or 7 may be asked to return to the CRU as soon as possible for an additional assessment. Sec. 8.3.7.	
AE/SAE Review	X	X>															X	All NSAEs and SAEs will be recorded up to 104-days postdose (inclusive). Sec. 8.4					
Laboratory																							
Procedures Serum hCG (WOCBP only)	X		X																	X		Appendices 2 and 8	
Serum FSH - (WONCBP only)	X																					Appendices 2, 5, and 8	
HIV, hepatitis B and C screen (per site SOP)	X																					Sec. 5.2, Appendices 2 and 8	

	1												Part	_								
		Scheduled Time  Day 1 (hours post-																				
			Da	•	(no dos		s pos	st-										]	Days			
Scheduled Timing	Screening 1	Screening 2 a	Predose	0	1	4	8	12	2 (D1 24 hrs)	3 (D1 48 hrs)	6 (D1 120 hrs) (±1 Day)	8 (D1 168 hrs)	11 (±1 Day)	14 (±1 Day)	21 (±2 Days)	28 (±3 Days)	42 (±4 Days)	60 (±5 Days)	90 (±5 Days)	120 Poststudy b (±5 Days)	134 Phone Follow-up c (±5 Days)	Notes
Drug and Alcohol Screen (per site SOP)	X		X																			Screening and predose drug/alcohol screen are mandatory (predose drug screen may occur in the evening prior to Day 1 at the time of admission); any additional drug/alcohol screen is conducted per site SOP. Sec. 8.3.5 and Appendix 2
Hematology and Chemistry	X	X d	X							X		X				X				X		Hematology/Chemistry will be obtained after an 8-hour fast. Predose tests can be conducted up to 24 hours prior to dosing. Sec. 8.3.5, Appendices 2 and 8
aPTT and PT at local lab	X							X		X	X	X	X			X						Sec. 5.2, 8.3.5, Appendices 2 and 8
Hemoccult test	Xe									X	X	X	X	X	X	X	X	X	X			Sec. 8.3.6

													Part	t 3								
		Scheduled Time																				
			Da	y 1	(ho		s po	st-		Days												
Scheduled Timing	Screening 1	Screening 2 a	Predose	0	1	4	8	12	2 (D1 24 hrs)	3 (D1 48 hrs)	6 (D1 120 hrs) (±1 Day)	8 (D1 168 hrs)	11 (±1 Day)	14 (±1 Day)	21 (±2 Days)	28 (±3 Days)	42 (±4 Days)	60 (±5 Days)	90 (±5 Days)	120 Poststudy b (±5 Days)	134 Phone Follow-up c (±5 Days)	Notes
Biomarkers																						
Blood for Genetic Analysis f			X																			Collected predose from enrolled participants only. Sec. 8.8.1, Appendix 8
Pharmacokinetics																						
Blood for Plasma MK- 2060			X		X			X	X	X	X	X	X	X	X	X	X	X	X	X		Sec. 8.6.1, Appendix 8, and Study Operations Manual
Pharmacodynamics																						
Blood for PT/aPTT/FXI activity by central lab			X		X			X	X	X	X	X	X	X	X	X	X	X	X	X		Sec. 8.7.1, Appendix 8, and Study Operations Manual
Blood for plasma ADA			X											X	X	X	X	X	X	X		Sec. 8.7.2, Appendix 8, and Study Operations Manual

	Part 3																					
	Scheduled Time																					
		Day 1 (hours post-dose)  Days																				
Scheduled Timing	Screening 1	Screening 2 a	Predose	0	1	4	8	12	2 (D1 24 hrs)	3 (D1 48 hrs)	6 (D1 120 hrs) (±1 Day)	8 (D1 168 hrs)	11 (±1 Day)	14 (±1 Day)	21 (±2 Days)	28 (±3 Days)	42 (±4 Days)	60 (±5 Days)	90 (±5 Days)	120 Poststudy b (±5 Days)	134 Phone Follow-up c (±5 Days)	Notes

ADA=antidrug antibody; aPTT=activated partial thromboplastin time; AE=adverse event; BMI=body mass index; BP=blood pressure; CRU=clinical research unit; D=Day; DNA=deoxyribonucleic acid, ECG=electrocardiogram; FBR=future biomedical research, FSH=follicle stimulating hormone; FXI=factor XI; HIV=human immunodeficiency virus; hCG=human chorionic gonadotropin; HR=heart rate; ID=identification; IEC=Independent Ethics Committee; IRB=Institutional Review Board; NSAE=nonserious adverse event; PT=prothrombin time; RR=respiratory rate; SAE=serious adverse event; SC=subcutaneous; SOP=standard operating procedure; VS=vital signs; WOCBP=women of childbearing potential; WONCBP=women of nonchildbearing potential

- a. Screening 2 should occur within 96 hours prior to Day 1. If Screening 1 occurs within 96 hrs prior to administration of the dose of study drug, Screening 2 is not required. b. The poststudy visit will occur approximately 120 days following administration of study drug. Procedures outlined in the poststudy visit may obtained on Day 120 (±5 days) Follow up on any clinical or laboratory AEs should occur in person if the poststudy visit occurs prior to 120 days following administration of study drug. If a participant discontinues for any reason at any time during the course of the study the participant may be asked to return to the clinic to complete the poststudy visit. The investigator may decide to perform the poststudy visit at the time of discontinuation or as soon as possible after discontinuation as outlined in Sections 7.1 and 8.1.9.
- c. At the discretion of the investigator an in-person follow-up may be performed.
- d. If Screening 2 occurs on Day -1, only obtain predose Hematology and Chemistry lab safety tests (these results will be used to satisfy both the Screening 2 and predose safety lab tests).
- e. Hemoccult test will be provided to a participant at Screening 1 visit and returned at Screening 2 visit or prior to dosing at the time scheduled by the investigator, if Screening 2 visit does not occur.
- f. This sample should be drawn for planned analysis of the association between genetic variants in DNA and drug response. This sample will not be collected at the site if there is either a local law or regulation prohibiting collection, or if the IRB/IEC does not approve the collection of the sample for this purpose. If the sample is collected, leftover extracted DNA will be stored for future biomedical research once the participant signs the FBR consent. If the planned genetic analysis is not approved, but FBR is approved and consent is given, this sample will be collected for the purpose of FBR. Blood for genetic analysis should be collected only once per participant after randomization.

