#### 1.3 Schedule of Activities

# 1.3.1 Part 1

Part 1																				
		Scheduled Time																		
		Day 1 (hours post-																		
					dos	se)	ı					1	1	1				ı	1	T
Scheduled Timing		Screening 2 a	Predose	0	1	4	8	12	2 (D1 24 hrs)	3 (D1 48 hrs)	6 (D1 120 hrs) (±1 Day)	8 (D1 168 hrs)	11 (±1 Day)	14 (±1 Day)	21 (±2 Days)	28 (±3 Days)	60 (±5 Days)	90 Poststudy b (±5 Days)	104 Phone Follow-up c (±5 Days)	Notes
Administrative Procedures																				
Informed Consent	X																			Sec. 5.1, 8.1.1.1
Informed Consent for FBR	X																			Sec. 5.1, 8.1.1.2
Inclusion/Exclusion Criteria	X	X	X																	Sec. 5.1, 5.2, 8.1.2
Participant ID Card	X																			Sec. 8.1.3
Participant ID Bracelet			X																	Sec. 8.11.2
Medical History	X	X	X																	Sec. 8.1.4
Assignment of Screening Number	X																			Sec. 8.1.6
Assignment of Randomization Number				X																The randomization number is assigned at the time of study drug administration. Sec. 5.5, 8.1.7
Prior/Concomitant Medication Review	X																		X	Sec. 5.2, 6.5, 8.1.5
Safety/Clinic Procedures																				
Full physical examination	X		X						X	X								X		Sec. 8.3.1, 8.3.7

											Pa	rt 1								
		1	_										Scho	edule	d Tin	ne				
			Da	ay 1	(ho		pos	t-				r		,		1	Da		T	
Scheduled Timing	Screening 1	Screening 2 a	Predose	0	1	4	8	12	2 (D1 24 hrs)	3 (D1 48 hrs)	6 (D1 120 hrs) (±1 Day)	8 (D1 168 hrs)	11 (±1 Day)	14 (±1 Day)	21 (±2 Days)	28 (±3 Days)	60 (±5 Days)	90 Poststudy b (±5 Days)	104 Phone Follow-up c (±5 Days)	Notes
Targeted physical examination																X	X			Sec. 8.3.1, Sec. 8.3.7
Height	X																			Sec. 8.3.1
Weight	X																	X		BMI to be taken only at Screening 1. Sec. 8.3.1
Orthostatic VS (HR, BP)	X		X								X									Sec. 8.3.2.2.
Semi-recumbent VS (HR, BP)	X		X-					-X		X	X		X			X	X	X		Day 1 measurements will be at predose, 1- and 12- hours postdose. Sec. 8.3.2
RR and body temperature	X		X		X			X		X	X		X					X		Sec. 8.3.2.
12-lead ECG	X		X					X		X	X		X					X		Sec. 8.3.3.
Standard Meals					Х	ζ			-X											Sec. 5.3.1.
Domiciling			X							-X										Sec. 8.1.11
MK-2060/Placebo Administration				X																MK-2060/Placebo will be administered SC at Time 0. Refer to Sec. 6.2, 8.1.8 and the Study Pharmacy Manual for additional information on the preparation and administration of the study drug.

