Informed Consent	X																					Sec. 5.1, 8.1.1.1
Informed Consent for FBR	X																					Sec. 5.1, 8.1.1.2
Inclusion/Exclusion Criteria	X	X	X																			Sec. 5.1, 5.2, 8.1.2
Participant ID Card	X																					Sec. 8.1.3
Participant ID Bracelet			X																			Sec. 8.11.2
Medical History	X	X	X																			Sec. 8.1.4
Assignment of Screening Number	X																					Sec. 8.1.6
Assignment of Randomization Number			X																			The randomization number is assigned at the time of study drug administration. Sec. 5.5, 8.1.7

												Part 2	2									
	≤28	eening 8 days Day 1								Int	erve	ntion	1								Post- study	Notes
Scheduled Timing (Week)	Screening 1	Screening 2 a		We	ek 1		We 2		We 3		W	∕eek ∙	4			Pos	st W	'eek	4			
Scheduled Timing (Day)			1	2	3	4	8	10	15	17	22	23	26	29	35	42	49	63	81	111	130	
Visit Window (Day)			NA	NA	NA	NA	NA	±1	NA	±1	NA	NA	±1	NA	±2	±2	±2	±2	±3	±3	±7	
Prior/Concomitant Medication Review	X																				X	Sec. 5.2, 6.5, 8.1.5
Safety/Clinic Procedures																						
Full physical examination	X		X				X		X		X			X							X	Sec. 8.3.1, 8.3.7
Targeted physical examination				X	X										X		X	X	X			Sec. 8.3.1, Sec. 8.3.7
Height	X																					Sec. 8.3.1
Weight	X																				X	BMI to be taken only at Screening 1. Sec. 8.3.1
Orthostatic VS (HR, BP)	X		X			X	X		X		X											Days 1, 4, 8, 15 and 22 measurements will be predose; Sec. 8.3.2.2.
Semi-recumbent VS (HR, BP)	X	X	X			X	X		X		X		X	X		X		X			X	Days 1, 4, 8, 15 and 22 measurements will be predose; Sec. 8.3.2
RR and body temperature	X		X			X	X		X		X											Days 1, 4, 8, 15 and 22 measurements will be predose; Sec. 8.3.2.

												Part 2	2									
	≤28	eening 8 days Day 1								Int	erve	ntion	ļ								Post- study	Notes
Scheduled Timing (Week)	Screening 1	Screening 2 a		We	ek 1		We 2		We 3		W	√eek 4	4			Pos	t W	eek	4			
Scheduled Timing (Day)			1	2	3	4	8	10	15	17	22	23	26	29	35	42	49	63	81	111	130	
Visit Window (Day)			NA	NA	NA	NA	NA	±1	NA	±1	NA	NA	±1	NA	±2	±2	±2	±2	±3	±3	±7	
12-lead ECG	X		X			X	X		X		X			X							X	Days 1, 4, 8, 15 and 22 measurements will be predose; Sec. 8.3.3.
Domiciling			X	X	X	X	X		X		X											Sec. 8.1.11.
Standard Meals			X				X		X		X											Sec. 5.3.1.

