#### 4.2.1 **Rationale for Endpoints**

#### 4.2.1.1 **Safety Endpoints**

Based on the data from P001 (healthy participant study), P004 (ESKD on HD study), P008 (ESKD on HD coadministered with Clopidogrel), and P007 (ongoing Phase 2 study in ESKD on HD with AVG) along with preclinical safety data, it is expected that single dose SC administration of MK-2060 will be well-tolerated in participants with CKD and ESKD. Physical examinations, VS, ECGs, laboratory safety tests (serum chemistry and hematology), aPTT, PT, and AEs related to bleeding will be assessed throughout the treatment period. AEs, including local infusion site reactions and systemic reactions to MK-2060 infusion, will be assessed throughout the treatment period.

08V5WO

Bleeding related AEs will include any sign or symptom of bleeding, even if not requiring intervention by a medical/healthcare professional, as well as clinically relevant nonmajor bleeding or major bleeding. As with all biologic medications, MK-2060 carries a risk of acute reactions upon exposure. These reactions can be categorized as common injection reactions, hypersensitivity reactions, and high cytokine release reactions. Acute reactions are usually mild, can occur even with the first dose, and can manifest with rigors, back pain, abdominal pain, nausea, vomiting, diarrhea, dyspnea, flushing, pruritus, and changes in heart rate or blood pressure. Acute hypersensitivity reactions typically occur after repeated exposures but can occur with the first dose. In addition to signs similar to common infusion reactions, participants may develop urticaria, wheezing, coughing, facial swelling, angioedema and more significant changes in VS. Cytokine release reactions are exceedingly rare but severe. They manifest as severe headache, nausea, vomiting, back pain, fever, hypotension and multiorgan failure. The risk of any of these reactions to MK-2060 is considered low given its profile in preclinical safety studies. There were no infusion reactions, no acute hypersensitivity reactions, and no cytokine release reactions observed thus far in any MK-2060 clinical studies. See the IB for more information on the Phase 1 clinical study experience with MK-2060.

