## 6.1 Study Intervention(s) Administered

The study interventions to be used in this study are outlined in Table 1.

Country-specific requirements are noted in Appendix 7.

Table 1 Study Interventions

Arm Name	Arm Type	Intervention Name	Intervention Type	Dose Formulation	Unit Dose Strength(s)	Dosage Level(s)	Route of Administration	Regimen/ Treatment Period/ Vaccination Regimen	Use	IMP or NIMP/ AxMP	Sourcing
MK-2060	Experimental	MK-2060	Drug	Powder	15 mg/mL	30 mg	SC	Part 1: Day 1 Part 2: Days 1, 2, 3, 4, 8, 15, and 22 Part 3: Day 1	Test Product	IMP	Provided by Sponsor
Placebo	Placebo Comparator	Placebo	Drug	Solution	Saline	0 mg	SC	Part 1: Day 1 Part 2: Days 1, 2, 3, 4, 8, 15, and 22	Placebo	IMP	Locally

EEA=European Economic Area; IMP=investigational medicinal product; NIMP/AxMP=noninvestigational/auxiliary medicinal product; SC=subcutaneous.

The classification of IMP and NIMP/AxMP in this table is based on guidance issued by the European Commission and applies to countries in the EEA. Country differences with respect to the definition/classification of IMP and NIMP/AxMP may exist. In these circumstances, local legislation is followed.

In this protocol, placebo is diluent alone (normal saline); diluent is used for blinding purposes and does not contain active ingredients.

All supplies indicated in Table 1 will be provided per the "Sourcing" column depending on local country operational requirements. If local sourcing, every attempt should be made to source these supplies from a single lot/batch number where possible (eg, not applicable in the case where multiple lots or batches may be required due to the length of the study, etc).

Refer to Section 8.1.8 for details regarding administration of the study intervention.

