#### 8.1.11 Domiciling

08V5WO

For Parts 1 and 3 participants will report to the CRU the evening before the scheduled day of study intervention administration for each treatment period. Participants will remain in the unit until at least 48-hours postdose. For Part 2 participants will report to the CRU the evening before the scheduled day of study intervention administration on Day 1 and will remain in the unit until the completion of off all postdose procedures on Day 4 (at least 4 hours). For the remaining dosing days in Part 2, at the discretion of the investigator the participants will return to the CRU either the evening before the scheduled day of study intervention administration or the morning of the scheduled day of study intervention administration (Days 8, 15 and 22) and will remain in the unit overnight until the completion of all postdose procedures the following day (at least 4 hours). At the discretion of the investigator, participants may be requested to remain in the CRU longer.

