#### 8.3.8 Management of Injection Reaction During and Post-Dose

As outlined in IB, the risk of injection reactions to MK-2060 is considered low since the molecule contains primarily human sequences. However, injection reactions may be observed. Since the purpose of the study is to characterize the safety profile of MK-2060, no prophylactic premedications to reduce the risk of injection reactions will be given prior to MK-2060 administration.

In rare instances, systemic injection reactions are severe and may have a fatal outcome. It is likely that most injection reactions will occur within the first 30 to 60 minutes of administration, though they may be observed up to 24 to 30 hours postdose. An anaphylactic reaction is a severe type of injection reaction that is characterized by cutaneous and mucosal symptoms, such as generalized hives, pruritus or flushing, swollen lips-tongue-uvula and angioedema, accompanied by respiratory compromise (bronchospasm, stridor or hoarseness) and/or changes in blood pressure (hypotension). Severe injection reactions, including cytokine release syndrome and hypersensitivity reactions must be promptly treated with interruption of the injection, medical management, appropriate monitoring, and life-saving measures. Appropriate resuscitation equipment and a physician should be readily available during the period of drug administration.

All participants should be evaluated for injection-type reactions. Participants should be carefully observed until complete resolution of all signs and symptoms, if a reaction occurs. Report any adverse experiences according to the guidelines in Section 8.4.

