#### 8.3.8.1 Systemic Injection Reaction Assessment

Participants will be monitored during the administration of MK-2060/placebo and for at least 4 hours and up to 24 to 48 hours postdose at the CRU after the initiation of administration. During this time, signs and symptoms of a systemic injection reaction, including but not limited to fever, VS changes (tachycardia/hypotension), pruritis, urticarial (hives), lip swelling, angioedema, bronchospasm, stridor, hoarseness, and shortness of breath will be monitored. Injection reactions must be assessed and managed promptly. Such assessment and management are discussed in Section 8.3.7.

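### Part 2 schedules no same-day postdose vital signs or temperature after any of its 7 doses, although other sections presume such readings and Parts 1 and 3 schedule them

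*Combined protocol and SAP*

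**What the plan says.** Table 1 in Section 6.1 gives the regimen as "Part 2: Days 1, 2, 3, 4, 8, 15, and 22", which is 7 doses.

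In the Part 2 SoA (1.3.2), the orthostatic, semi-recumbent HR/BP and RR/temperature rows all carry the note "Days 1, 4, 8, 15 and 22 measurements will be predose". None of these rows is marked on dosing Days 2 or 3. The last mark in the RR/temperature row is Day 22, predose.

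Other sections read as if postdose readings exist:

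- **8.3.8.1:** "Participants will be monitored during the administration of MK-2060/placebo and for at least 4 hours and up to 24 to 48 hours postdose". The signs to be watched are given as "including but not limited to fever, VS changes (tachycardia/hypotension", among others. No measurement times are set.
- **8.3.8:** most reactions are expected 30 to 60 minutes after administration, "though they may be observed up to 24 to 30 hours postdose".
- **8.3.2.1:** vital signs are taken at the SoA time points. In the same paragraph that sets the baseline for Parts 1, 2 and 3, postdose vital signs are described as single measurements.
- **8.11.6:** time windows are set for postdose vital signs, including readings before 24 h.
- **1.3.1 and 1.3.3:** in Part 1 the HR/BP note reads "Day 1 measurements will be at predose, 1- and 12- hours postdose", and the RR/temperature row is also marked at 1 h and 12 h. Part 3 is the same.
- **9.6:** vital signs and their change from baseline are summarised as deemed clinically appropriate.

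**The concern.** Part 2 is the only part with repeated dosing. Section 4.2.1.1 says of biologics in general: "Acute hypersensitivity reactions typically occur after repeated exposures but can occur with the first dose". Yet Part 2 is the part with no scheduled vital signs or temperature in the hours after a dose. A site could follow the SoA fully and record no postdose HR, BP, RR or temperature on any dosing day.

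The cost falls on the vital-sign data. The Part 2 change-from-baseline summaries would consist of predose values and later outpatient values, in both the MK-2060 and placebo groups. They could not describe an acute effect or support a statement that there was none.

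**Working it through.** **Inputs.** Dosing days are from Table 1 (6.1) and the SoA administration row. Reading days are from the Part 2 SoA:

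- HR/BP: Screening 1 and 2, and Days 1, 4, 8, 15, 22, 26, 29, 42, 63 and 130.
- RR/temperature: Screening 1, and Days 1, 4, 8, 15 and 22.
- Readings on Days 1, 4, 8, 15 and 22 are predose.
- Section 8.1.8.1 places all dosing in the morning.

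**Formula.** Hours to next reading = (day of next scheduled reading − dosing day) × 24. This assumes similar clock times each day.

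| Dose | Day | Reading on that day | Next HR/BP | Hours | Next RR/temperature | Hours |
|---|---|---|---|---|---|---|
| 1 | 1 | predose | Day 4 | (4−1)×24 = 72 | Day 4 | 72 |
| 2 | 2 | none | Day 4 | (4−2)×24 = 48 | Day 4 | 48 |
| 3 | 3 | none | Day 4 | (4−3)×24 = 24 | Day 4 | 24 |
| 4 | 4 | predose | Day 8 | (8−4)×24 = 96 | Day 8 | 96 |
| 5 | 8 | predose | Day 15 | (15−8)×24 = 168 | Day 15 | 168 |
| 6 | 15 | predose | Day 22 | (22−15)×24 = 168 | Day 22 | 168 |
| 7 | 22 | predose | Day 26 | (26−22)×24 = 96 | none | – |

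**Counts.**

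- Same-day postdose readings: 0 of 7 doses.
- HR/BP at about 24 h: 1 of 7 (dose 3). By about 48 h: 2 of 7 (doses 2 and 3). Both rest on the same Day 4 predose reading, which is also the first after dose 1.
- RR/temperature after dose 7: none.
- Parts 1 and 3: two readings (1 h and 12 h) within 12 h of the only dose.

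**Sensitivity to timing.** Section 8.11.6 allows a 3 h predose window on Days 8, 15 and 22 and gives none for Day 4. If 3 h also applied on Day 4, the interval after dose 3 could be 24 − 3 = 21 h. Day 26 has a window of ±1 day in the SoA, so the interval after dose 7 runs from 96 − 24 = 72 h to 96 + 24 = 120 h. Neither shift creates a same-day reading.

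**What the summaries would contain.** Baseline for HR/BP is the median of the Day 1 predose triplicate (8.3.2.1). Scheduled post-baseline values are nine for HR/BP (Days 4, 8, 15, 22, 26, 29, 42, 63 and 130) and four for RR/temperature (Days 4, 8, 15 and 22). The closest to any preceding dose is Day 4, about 24 h after dose 3.

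**The case against.** The strongest reply is that postdose monitoring is already mandatory. Section 8.3.8.1 applies to all parts, names fever and vital-sign changes, and requires at least 4 h of monitoring. Section 8.3.8 adds evaluation for reactions, observation until they resolve, and reporting. Six of the 7 doses are followed by at least one night in the unit (8.1.11), injection sites are examined on every dosing day, and AE review is continuous. All of this stands, and it limits the point to scheduled and recorded measurement. It does not remove the gap: 8.3.8.1 gives no times, and 8.3.2.1 defers to an SoA that has none. Section 8.11.7 lets timing change but says such changes will not increase the number of procedures. The windows in 8.11.6 are not specific to a part, so they could be read as serving Parts 1 and 3 alone. The reference to Part 2 in 8.3.2.1 is harder to read that way.

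Four stronger readings are tempting, and the documents do not support them:

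- **No reading after any dose.** HR/BP is scheduled at some later time after every dose, including Days 26 and 29 after the last.
- **The primary objective cannot be met.** The primary safety endpoints are bleeding-related AEs, AEs and discontinuations due to AEs (Sections 3 and 9.4), not vital signs. A clinically significant abnormal vital sign is itself an AE under Appendix 3.
- **The release on Day 4 contradicts the reaction window.** Section 8.1.11 keeps participants until postdose procedures are complete "on Day 4 (at least 4 hours"), which matches the 4 h minimum in 8.3.8.1. The 24 to 30 h in 8.3.8 says how late reactions may be seen and does not set a length of stay. The investigator may also extend the stay.
- **A raised hypersensitivity risk with this product.** The sentence in 4.2.1.1 is general. The same section calls the risk with MK-2060 low and reports no such reactions so far. Of the completed studies described, however, those with repeated dosing (P004 and P008) were intravenous, so they do not settle repeated subcutaneous dosing.

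**Conclusion.** The point holds as an inconsistency between the Part 2 SoA and the text of Section 8. Scheduled same-day postdose HR/BP, RR and temperature follow 0 of 7 doses. The next HR/BP is about 24 to 168 h later, and no RR or temperature follows the Day 22 dose. The hours assume morning dosing at similar times and predose readings close to the dose; the same-day count does not depend on exact times. The consequence is a Part 2 vital-sign dataset with no scheduled acute postdose values. Participants are not left unobserved, and AE capture is not lost. Severity is moderate: a cheap improvement, not a must-fix.

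**What to change.** Reconcile the Part 2 SoA with 8.3.2.1, 8.3.8.1 and 8.11.6. The SoA should show postdose HR/BP, RR and temperature time points for the Part 2 dosing days, chosen by the sponsor and placed within the stay of at least 4 h already required, including RR and temperature after the last dose. State the Day 4 predose window in 8.11.6, which now lists only Days 1, 8, 15 and 22.

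As a separate drafting point, 8.1.11 refers to postdose procedures on the day after the Day 8 and Day 15 doses, but the SoA has no Day 9 or Day 16. One of the two should be corrected.

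The cost is SoA wording and a few minutes of measurement per dose, while participants are already resting semi-recumbent in the unit for 4 h (8.1.8.1). The same-day readings need no new visit or staff.
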